LS	least squares
MCID	minimal clinically important difference
MCMC	Markov Chain Monte Carlo
MedDRA	Medical Dictionary for Regulatory Activities
MFNS	mometasone furoate nasal spray
MI	multiple imputation
MMRM	mixed-effects model with repeated measures
NC	nasal congestion
nNO	nasal nitric oxide
NP	nasal polyps
NPS	nasal polyp score
OR	odds ratio
PD	pharmacodynamics
PGx	pharmacogenetics
PM	evening
PK	pharmacokinetics
PT	preferred term
QD	once daily
QOL	quality of life
QTcF	Fridericia's correction formula for QT interval

Abbreviation	Definition
REML	restricted maximum-likelihood
SAE	serious adverse event
SAP	statistical analysis plan
SD	standard deviation
SE	standard error
SNOT-22	Sino-Nasal Outcome Test
SoA	schedule of activities
SOC	system organ class
TEAE	treatment-emergent adverse event
TSS	total symptom score
ULN	upper limit of normal
UPSIT	University of Pennsylvania Smell Identification Test
VAS	visual analog scale
WHO	World Health Organization

1. PURPOSE OF THE ANALYSIS

This statistical analysis plan (SAP) provides a comprehensive and detailed description of the statistical methodology to be used for reporting of the study results for use in the clinical study report (CSR) and is based on protocol version 5.0. The purpose of this SAP is to describe the methodology, procedures, rules, and conventions to be used for the reporting of results. Results to be reported will include summaries of subject disposition, demographic and baseline characteristics, significant protocol deviations, prior and concomitant medications, study treatment exposure and compliance, primary, secondary, and select tertiary/exploratory efficacy endpoints, pharmacokinetic (PK) concentrations, and safety endpoints, including adverse events (AEs), serious AEs (SAEs), and laboratory, vital sign, and electrocardiogram (ECG) parameters.

If additional analyses are required to supplement the planned analyses described in this SAP, they may be completed and will be identified in the CSR as post hoc.

The last two “Exploratory” objectives and endpoints in [Section 2.1](#) will not be addressed in this SAP.

This SAP was written with due consideration of the recommendations outlined in the most recent International Conference on Harmonisation (ICH) E9 Guideline ([ICH E9, 1998](#)) entitled Guidance for Industry E9 Statistical Principles for Clinical Trials and the most recent ICH E3 Guideline ([ICH E3, 1995](#)) entitled Guidance for Industry Structure and Content of Clinical Study Reports and was finalized prior to study unblinding.

In this document, investigational product (IP) and study treatment have the same meaning.

2. PROTOCOL SUMMARY

2.1. Objectives and Endpoints

The purpose of this Phase 2a study is to evaluate the efficacy, safety, PK, and pharmacodynamic (PD) of GB001 compared with placebo in patients with chronic rhinosinusitis (CRS) with or without bilateral nasal polyps (NP). The primary, secondary, and exploratory objectives and endpoints are as follows:

Objectives	Endpoints
Primary	

To evaluate the effect of GB001 on the Sino-Nasal Outcome Test-22 (SNOT-22)	
Change from baseline to Week 16 in SNOT-22
Secondary	

To evaluate the effect of GB001 on reducing opacification of the sinuses as measured by computed tomography (CT) scan	
Change from baseline to Week 16 in opacification of sinuses as measured by Lund-Mackay score on CT scan

To evaluate the effect of GB001 in the treatment of bilateral NP by assessment of the endoscopic nasal polyp score (NPS) in a subset of patients with nasal polyps	
Change from baseline to Week 16 in NPSTime to first response (≥ 1 point improvement from baseline) in NPS

To evaluate the effect of GB001 in improving patient reported symptoms	
Change from baseline to Week 16 in nasal congestion (NC)Change from baseline to Week 16 in total symptom score (TSS)

To evaluate the effect of GB001 in improving sense of smell (University of Pennsylvania Smell Identification Test, UPSIT)	
Change from baseline to Week 16 in UPSIT

To evaluate the effect of GB001 on chronic rhinosinusitis (CRS) exacerbation	
Time to first CRS exacerbation, defined as deterioration of CRS symptoms requiring treatment with an antibiotic, an anti-inflammatory drug, or a symptom reliever; an Emergency Department visit; or hospitalization

To evaluate the safety and tolerability of GB001 compared with placebo	
Incidence of treatment-emergent adverse events (TEAEs)Change from baseline in laboratory, electrocardiogram (ECG), and vital signs parameters

Exploratory	
• To evaluate the effect of GB001 on symptom improvement as measured by a visual analog scale (VAS)	• Change from baseline to Week 16 in VAS
• To evaluate the effect of GB001 on CRS exacerbation rate	• Annualized rate of CRS exacerbations
• To evaluate the effect of GB001 on maxillary CT opacification	• Change from baseline to Week 16 in percentage of maxillary sinus volume occupied by disease on CT scan
• To evaluate the effect of GB001 on worsening of CRS requiring the use of antibiotics	• Proportion of subjects with antibiotic use due to worsening CRS by Week 16
• To evaluate PK of GB001	• Plasma concentration of GB001
• To evaluate the effect of intervention on, as a function of, the PD markers	• Correlation between baseline markers and safety, tolerability, and efficacy parameters • Change in PD markers over time
• To evaluate the relationship between safety, efficacy, and exposure parameters and pharmacogenetics (PGx)	• Correlation between baseline characteristics and single nucleotide polymorphisms • Change from baseline in safety, efficacy, and exposure parameters as a function of single nucleotide polymorphisms

Additional efficacy endpoints not defined in the protocol but defined in this SAP include:

- Proportion of subjects with a ≥ 9 point decrease from baseline at Week 16 in SNOT-22 total score
- Proportion of subjects with a reduction from baseline of ≥ 1 in NPS at Weeks 8 and 16
- Change from baseline to Week 16 in anterior rhinorrhea, posterior rhinorrhea, and loss of sense of smell scores
- Change from baseline to Week 16 in volume of the air, volume of mucosa, and thickness of lateral wall
- Change from baseline to Week 16 in Asthma Control Questionnaire (ACQ-5) score.

2.2. Overall Study Design and Plan

This is a Phase 2a, randomized, double-blind, placebo-controlled, multi-center study to evaluate GB001 administered once a day for 16 weeks in subjects with CRS with or without bilateral NP. All subjects will be maintained on a stable background therapy of mometasone furoate nasal spray (MFNS) for the duration of the study.

The study will commence with a Screening visit (Visit 1), at which time informed consent will be obtained and inclusion and exclusion criteria will be assessed. Informed consent may be

obtained prior to the day of the Screening visit to allow for medication washouts or for other logistical reasons such as obtaining documentation of exacerbations, if necessary. All other screening procedures should be completed, where possible, on the day of the Screening visit. Subjects not meeting the eligibility criteria will be deemed screen failures and will not continue participation in the study. The Run-in period commences with completion of all Screening visit procedures and concludes at the Randomization visit (Visit 2). During the Run-in period of up to 4 weeks, subjects will capture nasal symptoms and MFNS use in an online daily Diary (morning [AM] and evening [PM]):

- Subject's treatment regimen with MFNS should remain stable.
- 2 actuations (50 µg/actuation) in each nostril twice daily (BID; total daily dose of 400 µg), unless subject is intolerant to a BID regimen of MFNS in which case, they can stay on the dose regimen in place prior to screening.
- The only dose modification of MFNS during the Run-in period may be for subjects who were switched from another intranasal corticosteroids (INCS) to MFNS and need to change to a once daily (QD) regimen due to intolerance.

After the Randomization visit, subjects will enter the Double-Blind, Placebo-Controlled period which will be followed by a Follow-up period.

Total duration for study participation per subject is up to 24 weeks (includes a Screening visit; followed by an up to 4-week Run-in period to allow for collection of baseline Diary data and standardized MFNS treatment regimen; a 16-week Double-Blind, Placebo-Controlled period; and a 4-week Follow-up period).

Subjects who permanently discontinue IP or withdraw early from the study will be requested to attend the Early Discontinuation of IP visit or Early Withdrawal (EW) visit, as appropriate, and will be strongly encouraged to complete any remaining study visits as per the Schedule of Activities (SoA).

The first dose of double-blind IP will be administered in the clinic on Day 1. All subsequent doses will be taken orally, in the AM on an empty stomach. Following initiation of IP, subjects will visit the clinic for assessments per protocol. Subjects will continue on mometasone furoate: MFNS two actuations in each nostril BID (or QD in case subject cannot tolerate the high dose) during the course of the study.

All subjects will complete a daily Diary from the Screening visit through the Follow-up visit, responding to the AM and PM CRS symptom questions and documenting twice daily MFNS use.

The protocol contains further details related to the study design and conduct.

2.3. Study Population

The study population is comprised of: symptomatic subjects with CRS without NP (CRSsNP), defined as an absence of NP based on visual examination or an NPS of 0 based on nasal endoscopy, and evidence of an eosinophilic phenotype, defined as a blood eosinophil count of

≥ 250 cells/ μ L; and symptomatic subjects with CRS with NP (CRSwNP), defined as a minimum NPS of 4 out of a maximum of 8, with at least a score of 2 for each nostril, as assessed by endoscopic diagnosis by a blinded central reader. Subjects will be male or female and ≥ 18 to 75 years of age at the time of the Screening visit. Subjects with historical evidence of neutrophilic predominant polyp disease will be excluded considering that the mechanism of action of GB001 is thought to be linked to eosinophilic Type 2 inflammation.

2.4. Randomization and Treatment Regimens

This study will randomize approximately 100 subjects, with approximately 50 subjects per treatment group, randomized in a 1:1 ratio to the following treatment groups:

- GB001 40 mg QD
- Matching placebo QD

Randomization will be stratified by country, the presence or absence of NP (CRSwNP and CRSsNP), and the presence or absence of comorbid asthma among CRSwNP subjects. Presence of NP is defined by a minimum NPS of 4 out of a maximum score of 8 with a score of at least 2 for each nostril. Absence of NP is defined as an absence of NP based on visual examination or an NPS of 0 based on nasal endoscopy. Presence of comorbid asthma is defined as a diagnosis of asthma by a physician according to Global Initiative for Asthma (GINA) guidelines at screening or prior to study entry. The CRSwNP stratum will consist of approximately 64 subjects, and the CRSsNP stratum will consist of approximately 36 subjects.

2.5. Sample Size Determination

A total sample size of approximately 100 subjects (approximately 50 per treatment group, randomized in a 1:1 ratio) is estimated to provide approximately 90% power to detect a treatment difference of 12.0 between GB001 and placebo at a 0.050 two-sided level of significance for the primary endpoint of change from baseline to Week 16 in SNOT-22 score, assuming a common standard deviation (SD) of 16.8 and a dropout rate of 15% using a two-sided t-test.

A total sample size of approximately 64 subjects in the CRSwNP stratum (approximately 32 per treatment group, randomized in a 1:1 ratio) is estimated to provide approximately 80% power to detect a treatment difference of 1.3 between GB001 and placebo at a 0.050 two-sided level of significance for the secondary endpoint of change from baseline to Week 16 in NPS, assuming a common SD of 1.7 and a dropout rate of 15% using a two-sided t-test.

Therefore, the total sample size of approximately 100 subjects overall will consist of approximately 64 subjects in the CRSwNP stratum and 36 subjects in the CRSsNP stratum.

3. GENERAL ANALYSIS AND REPORTING CONVENTIONS

All analyses will be performed using SAS® System (SAS Institute Inc., Cary, NC) version 9.4 or later.

Categorical variables will be summarized using counts (n) and percentages (%) and will be presented in the format “n (xx.x)”. If a count is 0, no percentage will be shown. To ensure completeness, summaries for categorical and discrete variables may include all categories, even if no subjects had a value in a particular category. Additionally, for missing data, a category of “Missing” will be presented as needed.

Continuous variables, unless otherwise stated, will be summarized using descriptive statistics: number of subjects with non-missing data (n), mean, standard deviation (SD), median, 25th and 75th percentiles, minimum, and maximum. Descriptive statistics on select measures may also include the standard error (SE) and 95% confidence interval (CI) for the mean. In general, rounding rules for reporting continuous descriptive summary statistics are as follows:

- If the original values have 0 or 1 decimal places: mean, median, 25th and 75th percentiles will be reported to one more decimal place than the original values, and SD and SE will be reported to 2 more decimal places than the original values
- If the original values have 2 or more decimal places: mean, median, 25th and 75th percentiles, SD, and SE will all be reported to 3 decimal places

Minimum and maximum will always be reported to the same decimal places as the original values, up to a maximum of 3 decimal places. Percent change from baseline will be reported to 1 more decimal place than change from baseline, up to a maximum of 3 decimal places.

Efficacy results will be summarized by various measures including but not limited to least squares (LS) means, differences in LS means, SEs, odds ratios (ORs), hazard ratios, rate ratios, p-values, and two-sided 95% CIs. The SEs, LS means, differences in LS means and corresponding CIs will be reported per the rules above, with the CIs following the same rounding rules as the mean, ORs, hazard ratios, rate ratios, and corresponding CIs will be reported to 3 decimal places, and percentage reductions and corresponding CIs will be reported to 1 decimal place. P-values will be reported to 4 decimal places, with values less than 0.0001 displayed as < 0.0001 and values greater than 0.9999 displayed as > 0.9999. All statistical hypothesis testing will be at an 0.050 two-sided level of significance.

In general, all analyses will be performed for the overall population, with the exception of efficacy endpoints based on NPS, which will be performed only for the randomized CRSwNP subgroup.

Disposition, demographic and baseline characteristics, significant protocol deviations, and medical history tables will be presented by randomized treatment group and will include an overall column combining both treatment groups. Prior and concomitant medication tables will be presented by either randomized treatment group or actual treatment group, depending on the analysis, and will include an overall column combining both treatment groups. Select analyses among these will be performed for the randomized CRSwNP and CRSsNP subgroups.

Efficacy tables will be presented by randomized treatment group only and select efficacy analyses will be performed for the randomized CRSwNP and CRSsNP subgroups. Safety tables will be presented by actual treatment group and select safety analyses will be performed for the actual CRSwNP and CRSsNP subgroups.

When appropriate, sorting in disposition, demographic, and baseline characteristics tables will be based on decreasing incidence within the overall column. In general, AE tables that are displayed by system organ class (SOC) and preferred term (PT) will be sorted by the internationally agreed order for SOC, and by decreasing incidence and then alphabetically for PT within the GB001 40 mg column. Otherwise, safety tables, when applicable, will be sorted by decreasing incidence within the GB001 40 mg column.

Assessments at the Randomization Visit are to be performed prior to the first dose of study treatment. Therefore, for all measures, the baseline value is defined as either the last non-missing value before the first dose of study treatment, the mean over the last 7 days of the Run-in period including the value on Day 1 (AM endpoints collected in the daily Diary), or the mean over the last 7 days of the Run-in period excluding the value on Day 1 (PM endpoints collected in the Diary).

If multiple evaluations occur on the same day, the average of these evaluations will be used for analysis excluding maximum post-baseline, abnormality, and outlier analyses.

For all shift from baseline analyses, percentages will be based on the number of subjects in each baseline category and also having at least one post-baseline measurement.

Values with “<” or “>” signs will be analyzed without the signs in tables and figures. In by-subject data listings, values will be reported as collected with the sign.

Dates in by-subject data listings will be displayed as yyyy-mm-dd (e.g., 2015-01-24). In general, by-subject data listings will be sorted by randomized treatment group and subject number.

3.1. Visit Windowing

Subjects do not always strictly adhere to the visit schedule timing in protocols. Therefore, the designation of visits (or timepoints) will generally be based on the actual day of evaluation relative to the date of first dose of study treatment (Day 1), rather than the nominal visit, for analyses conducted by visit.

Mutually exclusive visit windows containing no gaps will generally be utilized to assign visits for by visit analysis and will correspond to post-baseline visits specified in the protocol. Visits for analysis will be assigned by using a windowing scheme as described below.

The upper bound of the baseline visit window is Day 1 (up to the time of the first dose for assessments with time collected), and the lower bound of the first post-baseline visit window is Day 1 after the time of the first dose for assessments with time collected and Day 2 for assessments without time collected. For all other lower and upper bounds of visit windows, windows will end at the midpoint between scheduled visit timepoints, with the midpoint in the

latter visit window with the exception of the Week 16 visit for the efficacy endpoints, which will include Day 120 as the upper bound of the visit window.

If a subject's last observation is after the date of first dose of study treatment but prior to the first scheduled visit, data from an EW visit will be assigned to the first scheduled visit. If two or more evaluations occur in the same visit window, the evaluation closest to the target visit day will be selected for inclusion in the analysis. If multiple evaluations are equally close to the target visit day, then the latest evaluation will be selected for inclusion in the analysis. The target visit day for Week 1 and on is defined as the week number specified in the SoA of the protocol multiplied by 7 plus 1.

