Randomization will be stratified by country, the presence or absence of NP (CRSwNP and CRSsNP), and the presence or absence of comorbid asthma among CRSwNP subjects. Presence of NP is defined by a minimum NPS of 4 out of a maximum score of 8 with a score of at least 2 for each nostril. Absence of NP is defined as an absence of NP based on visual examination or an NPS of 0 based on nasal endoscopy. Presence of comorbid asthma is defined as a diagnosis of asthma by a physician according to Global Initiative for Asthma (GINA) guidelines at screening

or prior to study entry. The CRSwNP stratum will consist of approximately 64 subjects, and the CRSsNP stratum will consist of approximately 36 subjects.

Subjects will continue on mometasone furoate: MFNS two actuations in each nostril BID (or QD in case subject cannot tolerate the high dose) during the course of the study.

Following initiation of investigational product (IP) at the clinic, subjects will visit the clinic weekly for the first 6 weeks and approximately every 4 weeks thereafter through week 20, for a total of 10 additional visits (refer to Schedule of Activities, [Section 1.3](#)).

Early Discontinuation of IP and Early Withdrawal from Study: Subjects will be requested to attend the Early Discontinuation of IP or Early Withdrawal (EW) visit, as appropriate, and will be strongly encouraged to complete any remaining study visits as per the Schedule of Activities (SoA; [Section 1.3](#)). Subjects who permanently discontinue IP and continue in the study will complete the Early Discontinuation of IP visit at the time of IP discontinuation and then return for the next visit in the visit sequence. At the visits after the Early Discontinuation of IP visit, study procedures will be completed except for dispensation/return of IP. Subjects who withdraw early from the study, regardless of the reason, will be requested to return to the clinic to complete the EW visit. All subjects who remain on IP through and including Visit 7 (Week 16) or who complete the EW visit will be asked to return for a Follow-up visit approximately 4 weeks after their last dose of IP to assess subject safety.

Follow-up Period: Subjects can continue treatment with the stable dose of MFNS maintained over the Double-Blind, Placebo-Controlled period, or modify treatment based on medical judgment.

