9.2. Clinical Laboratory Evaluation

Actual values and change from baseline values for quantitative laboratory parameters (clinical and liver chemistry, hematology, and urinalysis) will be summarized by visit for the safety population.

Shift tables will be presented for clinical and liver chemistry, hematology, and qualitative urinalysis parameters summarizing shifts from baseline to high and low (or to abnormal for urinalysis) at any time post-baseline based on laboratory normal ranges.

A summary of maximum post-baseline values > 1.0 , > 1.5 , and $> 3.0 \text{ } 10^9/\text{L}$ for blood eosinophils will be presented.

Summaries of maximum post-baseline values for liver chemistry parameters (alanine aminotransferase [ALT], aspartate aminotransferase [AST], ALT or AST, concurrent ALT or AST and total bilirubin, total bilirubin, direct bilirubin, indirect bilirubin, alkaline phosphatase, gamma-glutamyl transferase [GGT]), and bile acid according to categories based on multiples of upper limit of normal (ULN) will be presented. Liver chemistry parameters according to categories based on multiples of ULN will also be presented by visit.

For laboratory shift tables and summaries of maximum post-baseline values, only subjects with at least one post-baseline value will be included.

The time to first elevation for ALT will be presented for subjects with an elevation in ALT. An elevation for ALT will be defined as the first post-baseline value $\geq 1.5 \times \text{ULN}$ for subjects with a baseline value $\leq \text{ULN}$, and the first post-baseline value with a $> 50\%$ increase from baseline for subjects with a baseline value $> \text{ULN}$. This analysis will also be repeated using a threshold of $> 1.0 \times \text{ULN}$. In addition, the time to first elevation of AST will be summarized in the same manner as described above for time to first elevation of ALT.

In addition, the following figures/plots will be provided:

- Mean change from baseline values, including SE bars, by visit figures for liver chemistry parameters
- Mean ratio of actual values to ULN, including SE bars, by visit figures for liver chemistry parameters
- Evaluation of Drug-Induced Serious Hepatotoxicity (eDISH) ([Merz, 2014](#)) plots

- Mean actual values and mean change from baseline values, including SE bars, by visit figures for blood eosinophils
- Maximum post-baseline values versus baseline values plot for blood eosinophils

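### SAP 3.1 has no rule for the Follow-up visit of early-withdrawn subjects, so some off-drug laboratory and vital sign values are filed under Weeks 1–16 and are missing from the Follow-up row

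*SAP*

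**What the plan says.** **Visit assignment (SAP 3.1).** With the hedge that this applies in general, timepoints are designated "based on the actual day of evaluation relative to the date of first dose of study treatment (Day 1), rather than the nominal visit". "Mutually exclusive visit windows containing no gaps will generally be utilized to assign visits for by visit analysis". Apart from the bounds around Day 1, "windows will end at the midpoint between scheduled visit timepoints". A midpoint day belongs to the later of the two windows, with one exception for efficacy: "latter visit window with the exception of the Week 16 visit for the efficacy endpoints, which will include Day 120 as the upper bound". The target day is "defined as the week number specified in the SoA of the protocol multiplied by 7 plus 1". If two evaluations share a window, the one nearer the target is used; a tie goes to the later one. The only early-withdrawal rule covers a subject whose last observation precedes the first scheduled visit: "data from an EW visit will be assigned to the first scheduled visit". The section does not mention the Follow-up visit or the date of last dose.

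**Timing of Follow-up (Protocol 4.1.1 and 1.3).** Subjects who stay on investigational product (IP) through Week 16, or who complete the Early Withdrawal (EW) visit, "will be asked to return for a Follow-up visit approximately 4 weeks after their last dose of IP to assess subject safety". The Schedule of Activities heads the column as following Week 16 or EW and gives its week as 20 or as needed. Clinical chemistry, hematology and vital signs are marked there.

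**Outputs (SAP 9.2 and 9.3.1).** Laboratory and vital sign values are summarized by visit. Liver chemistry is also shown by visit in categories of the upper limit of normal (ULN) and in figures, for example "Mean ratio of actual values to ULN, including SE bars, by visit figures for liver chemistry parameters".

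**The concern.** The two documents use different clocks. The protocol counts the Follow-up visit of a withdrawn subject from the last dose; the SAP counts every evaluation from the first dose. Because the windows leave no gaps, an early Follow-up visit must land in some week of the 16-week double-blind period unless the last dose came late.

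Protocol 2.3.1 names drug-induced liver injury as a potential risk, and the by-visit liver displays show its time course. A value taken about 4 weeks off drug would be tabulated beside values from subjects still being dosed. If it had returned to normal, it would pull that week's summary down slightly. The same subject would be missing from the Follow-up row, which is where a reader looks for off-drug recovery.

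**Working it through.** **Borrowed planning figure.** The plan gives no figure for this point. The size estimate below uses the 15% dropout in SAP 2.5. The sample size that rests on it reproduces: a difference of 12.0, SD 16.8 and 90% power need 42 per arm, and 84/(1 − 0.15) = 98.8, so 99 against about 100 stated.

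**Windows.** Target day = 7 × week + 1, so Week 6 = Day 43, Week 8 = Day 57, Week 12 = Day 85, Week 16 = Day 113 and Week 20 = Day 141. Midpoints are (43 + 57)/2 = 50, (57 + 85)/2 = 71, (85 + 113)/2 = 99 and (113 + 141)/2 = 127. The Day 120 cap is for efficacy only, so the safety Week 16 window runs to Day 126.

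**Cut-off.** With Follow-up on last dose + 28, the Week 20 window (Day 127 on) is reached only if the last dose is on Day 127 − 28 = Day 99 or later. With 25 or 31 days in place of 28, the last misplaced dose day is Day 101 or Day 95.

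**Where the others go (chemistry, scheduled at every visit).**

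| Last dose (day) | Follow-up (day) | Window | Share of Days 1–112 |
|---|---|---|---|
| 1–4 | 29–32 | Week 4 | 4/112 = 3.6% |
| 5–11 | 33–39 | Week 5 | 7/112 = 6.3% |
| 12–21 | 40–49 | Week 6 | 10/112 = 8.9% |
| 22–42 | 50–70 | Week 8 | 21/112 = 18.8% |
| 43–70 | 71–98 | Week 12 | 28/112 = 25% |
| 71–98 | 99–126 | Week 16 | 28/112 = 25% |
| 99–112 | 127–140 | Week 20 | 14/112 = 12.5% |

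So 98 of 112 possible last-dose days (87.5%; 85% to 90% with the tolerance) misplace the visit. A last dose on Day 50 gives Day 78, in Week 12. Vital signs have fewer early visits, so the split over Weeks 4–8 differs, but the Day 98 cut-off is the same.

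**Hematology.** After baseline the schedule has it at Weeks 8 and 16 and at Follow-up. If windows follow each test's own schedule, Week 8 covers Days 2–84 and Week 16 Days 85–126. With EW on Day 29 (taken as the last-dose day) and Follow-up on Day 57, both samples fall in Week 8. Distances to target are 28 and 0 days, so the off-drug sample is kept and the EW sample drops out of the by-visit table.

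**Size (chemistry).** Assume that all of the 15% withdraw from the study (7.5 of 50 per arm), that last-dose days are uniform over 112 days, and that everyone attends Follow-up. Then 7.5 × 0.875 = 6.6 Follow-up visits per arm are misplaced. Subjects still in the study number 50 − 7.5 × 8/16 = 46.25 at Week 8, 50 − 7.5 × 12/16 = 44.4 at Week 12 and 42.5 at Week 16. The misplaced shares are:
- Week 8: 7.5 × 0.1875 = 1.4; 1.4/(1.4 + 46.25) = 3.0%
- Week 12: 7.5 × 0.25 = 1.9; 1.9/(1.9 + 44.4) = 4.1%
- Week 16: 1.9/(1.9 + 42.5) = 4.2%

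**The case against.** The strongest reply is that Weeks 1–16 are not an on-treatment display. SAP 9.2 and 9.3.1 summarize all dosed subjects by visit. Protocol 4.1.1 and 7.1 encourage subjects who stop IP to keep attending, so off-drug values sit in those rows by design. Section 7.1 even lets the Week 16 visit serve as Follow-up for a subject who stopped before Week 12 and stayed in the study. This stands: a reader might infer that the rule contaminates an otherwise on-drug series, and the documents do not support that.

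A reader might also infer that subjects stopped for liver enzymes are the ones misfiled, hiding a liver signal. Table 6 in Protocol 10.6 keeps subjects who are not rechallenged in the study, so a liver stop alone does not trigger the early Follow-up visit; withdrawal from the study does. The liver outputs that do not depend on weekly windows also remain: maximum post-baseline values, concurrent elevations, any-time shifts, time to first ALT or AST elevation, eDISH plots, adverse event tables and listings.

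Finally, SAP 3.1 says its rule applies generally, so a programmer could treat Follow-up separately, and withdrawn subjects are only encouraged to attend. Both points are fair. But no alternative rule is written, and the text as it stands gives the result above. The objection limits the consequence; it does not remove the gap.

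**Conclusion.** The gap is real and its effect small. As written, the SAP places Follow-up laboratory and vital sign values of early-withdrawn subjects in a Week 1–16 row whenever the last dose was on or before about Day 98, and leaves those subjects out of the Follow-up row. What is lost is an accurate label: a visit defined by time since last dose is reported by time since first dose.

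The reach is confined to descriptive by-visit laboratory tables and figures, including the liver ULN categories, and by-visit vital signs. No safety hypothesis test rests on them. SNOT-22 is not scheduled at Follow-up, so the primary endpoint is untouched.

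The 3–4% is close to a ceiling for dropout and attendance, since it takes all of the planned dropout as study withdrawals who return. It also rests on uniform last-dose days; clustered withdrawals would concentrate the same few values in fewer rows. The actual number of withdrawals is not in the documents. The hematology example further assumes windows built from that test's own schedule, which SAP 3.1 does not spell out.

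**What to change.** Add one sentence to SAP 3.1: for by-visit safety summaries, evaluations collected at the nominal Follow-up visit are assigned to Follow-up regardless of study day and are not eligible for the Week 1–16 windows. Leave the windowing of all other scheduled and unscheduled evaluations as it is.

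It would be tempting also to limit the Week 1–16 windows to evaluations up to the Week 16, EW or Early Discontinuation visit, plus scheduled visits attended after IP is stopped. That should not be done. It would remove unscheduled liver retests after discontinuation from the weekly rows, while those rows would still mix on-drug and off-drug values.

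The cost is the sentence and a change to the visit-mapping program. The Week 1–16 rows lose a few values. The Follow-up row will pool different study days, though at a similar time since last dose; a table footnote can say so.
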